6.5. SAFETY ANALYSIS (TS)

This section will describe the data related to suspected adverse reactions linked to Spiolto® Respimat® (serious or non-serious) and/or adverse events not related to Spiolto® Respimat®, but with a fatal outcome, reported by patients during the course of the study.

Pregnancies will also be indicated, at the start and at the end of the study. The sample analysed will be the **Treated Set** (n=xxx, *see Table 4*).

Table 26. Adverse events (AE) overall summary - Treated Set (TS)	
	Total n (%)
Number of patients	
Patients with investigator defined drug-related AE	
Patients with investigator defined drug-related AE leading to discontinuation of trial drug	
Patients with serious AE	
Mortal	
Life-threatening	
Incapacity	
Hospitalisation	
Prolongation of hospitalisation	
Congenital anomaly	
Patients with serious AE leading to discontinuation	
Patients with serious drug-related AE	

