9.2.3 Study visits

Table 9.2.3:1: Visit flow chart and data collection parameters

Parameter	Visit 1; baseline visit	Visit 2; approx. 6 weeks after baseline visit
Informed Consent	X	
Inclusion / Exclusion Criteria	X	
Patient demographics (age, gender, height, and weight)	X	
Start of COPD	X	
Number of exacerbations in the last 12 months	X	
Number of exacerbations leading to hospitalization in the last 12 months	X	
mMRC breathlessness scale	X	
Past COPD therapies (6 months before visit 1)	X	
Respimat® training (yes/no)	X	
COPD severity based on GOLD assessment ¹	X	
Smoking status	X	X
Concomitant diseases / Comorbidities	X	X
COPD related and other relevant concomitant medication	X	X
Physical functioning (PF-10) questionnaire, completed by patient	X	X
General condition of patient evaluated by Physician's Global Evaluation (PGE)	X	X
Safety: Adverse Drug Reactions (serious and non-serious), fatal AE, pregnancy	X	X
Patient satisfaction with Spiolto® Respimat®, survey completed by the patient		X
Rational for Spiolto® Respimat® treatment discontinuation (if applicable)		X
Continuation or discontinuation of treatment with Spiolto® Respimat® after the study (yes/no)		X

Proprietary confidential information © 2016 Boehringer Ingelheim International GmbH or one or more of its affiliated companies

1 GOLD patient group (A, B, C or D) will be automatically calculated within the eCRF based on available exacerbation history, mMRC, and GOLD spirometric classification of airflow limitation based on post-bronchodilator FEV1 if available.

Baseline characteristics of patients being eligible and who gave Informed Consent, but were not treated in the study will also be collected.

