9.7 DATA ANALYSIS

9.7.1 Main analysis

In this non-interventional study, cross-sectional data at study baseline and longitudinal follow-up data over 6 weeks will be collected for patients with chronic obstructive pulmonary disease (COPD) requiring long-acting dual bronchodilation in routine clinical practice.

Baseline data will be described using a cross-sectional approach. Data from the longitudinal follow-up will be summarized descriptively. Due to the nature of this non-interventional study, there is no (confirmatory) hypothesis testing foreseen in a strict statistical sense. Analyses are descriptive in nature and confidence intervals and p-values from statistical models are used for exploratory purposes. No adjustments for multiple testing are made in the evaluation of statistical significance. Consequently, significant differences may be observed by chance alone and p-values should be interpreted as exploratory and with caution.

Details will be described in the statistical epidemiological analysis plan (SAP).

No formal hypothesis testing will be performed since this is a self-controlled study.

All patients who have received at least one dose of Spiolto® Respimat® will be included in the analysis; this is the treated set. All analyses will be performed on the treated set (as-treated analysis). If patients have missing values for an outcome, those patients will be excluded for that outcome's analysis.

The assessment will be carried out using SAS® software, 9.4 version or later. The statistical characteristics presented in the end-of-text tables will be N / mean / SD / min / median / max

for continuous variables. Tabulations of relative and absolute frequencies will be presented for categorical variables. Incidence rates and 95% CI will be given when appropriate.

The analyses will relate to the following data as recorded in the eCRF:

- Patient demographics (age, gender, height, and weight);
- Comorbidities;
- COPD related and other concomitant medication
- History of smoking
- Reported exacerbations
- Breathlessness based on mMRC score at visit 1
- Physical Functioning based on PF-10 scores (therapeutic success at visit 2); primary outcome
- Changes from visit 1 to visit 2 in the PF-10 score; secondary outcome
- Patient satisfaction with Spiolto® Respimat® at visit 2 only; secondary outcome
- General condition of the patient: evaluated by the physician (Physician's Global Evaluation (PGE)); secondary outcome

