11. MANAGEMENT AND REPORTING OF ADVERSE EVENTS & ADVERSE DRUG REACTIONS

11.1 Definitions of adverse events

Adverse event

An adverse event (AE) is defined as any untoward medical occurrence in a patient or clinical investigation subject administered a medicinal product and which does not necessarily have a causal relationship with this treatment. An adverse event can therefore be any unfavorable and unintended sign (e.g. an abnormal laboratory finding), symptom, or disease temporally associated with the use of a medicinal product, whether or not considered related to the medicinal product.

Adverse drug reaction

An adverse drug reaction (ADR) is defined as a response to a medicinal product which is noxious and unintended. Response in this context means that a causal relationship between a medicinal product and an adverse event is at least a reasonable possibility. Adverse drug reactions may arise from use of the product within or outside the terms of the marketing authorization or from occupational exposure. Conditions of use outside the marketing authorization include off-label use, overdose, misuse, abuse and medication errors.

Serious adverse event

A serious adverse event is defined as any AE which

- results in death,
- is life-threatening,
- requires in-patient hospitalization, or
- prolongation of existing hospitalization,
- results in persistent or significant disability or incapacity, or
- is a congenital anomaly/birth defect

Life-threatening in this context refers to a reaction in which the patient was at risk of death at the time of the reaction; it does not refer to a reaction that hypothetically might have caused death if more severe.

Medical and scientific judgment should be exercised in deciding whether other situations should be considered serious reactions, such as important medical events that might not be immediately life threatening or result in death or hospitalization but might jeopardize the patient or might require intervention to prevent one of the other outcomes listed above.

Examples of such events are intensive treatment in an emergency room or at home for allergic bronchospasm, blood dyscrasias or convulsions that do not result in hospitalization or development of dependency or abuse. Any suspected transmission via a medicinal product of an infectious agent is also considered a serious adverse reaction.

Adverse Event of Special Interest (AESI)

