11.2 Adverse event and serious adverse event collection and reporting

The investigator shall maintain and keep detailed records of all AEs in their patient files.

Collection of AEs

The study design is of non-interventional nature and the study is conducted within the conditions of the approved marketing authorisation. Sufficient data from controlled interventional trials are available to support the evidence on the safety and efficacy of the studied BI drug. For this reason the following AE collection and reporting requirements have been defined.

The following must be collected by the investigator in the eCRF from signing the informed consent onwards until the end of the study:

- all ADRs (serious and non-serious),
- all AEs with fatal outcome (serious adverse events),

Note: For all patients on these data must be recorded on the AE pages in the eCRF. The separate NIS (S)AE form must in addition be used and forwarded to the local Pharmacovigilance fax as indicated in the form.*

All ADRs, including those persisting after study completion must be followed up until they are resolved, have been sufficiently characterized, or no further information can be obtained.

The investigator carefully assesses whether an AE constitutes an ADR using the information below.

Causal relationship of adverse event

The definition of an adverse reaction implies at least a reasonable possibility of a causal relationship between a suspected medicinal product and an adverse event. An adverse reaction, in contrast to an adverse event, is characterized by the fact that a causal relationship between a medicinal product and an occurrence is suspected.

Medical judgment should be used to determine the relationship, considering all relevant factors, including pattern of reaction, temporal relationship, de-challenge or re-challenge, confounding factors such as concomitant medication, concomitant diseases and relevant history.

Arguments that may suggest a **reasonable causal relationship** could be:

- The event is **consistent with the known pharmacology** of the drug
- The event is known to be caused by **or attributed to the drug class**.
- **A plausible time to onset of the event** relative to the time of drug exposure.
- Evidence that the **event is reproducible** when the drug is re-introduced
- **No medically sound alternative etiologies** that could explain the event (e.g. preexisting or concomitant diseases, or co-medications).

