Proprietary confidential information © 2016 Boehringer Ingelheim International GmbH or one or more of its affiliated companies

The following must be reported by the investigator on the NIS (S)AE Form from signing the informed consent onwards until the end of the study:

Table 11.2:1 Reporting types and timelines

Type of Report*	Timeline
All SADRs associated with Spiolto® Respimat®	immediately within 24 hours
All AEs with fatal outcome in patients exposed to Spiolto® Respimat®	immediately within 24 hours
All non-serious ADRs associated with Spiolto® Respimat®	7 calendar days
All pregnancy monitoring forms associated with Spiolto® Respimat®	7 calendar days

The same timelines apply if follow-up information becomes available for the respective events. In specific occasions the Investigator could inform the Sponsor upfront via telephone. This does not replace the requirement to complete and fax/email the NIS (S)AE form.

Information required

For each reportable adverse event, the investigator should provide the information requested on the appropriate eCRF pages and the NIS (S)AE form.

Reporting of related Adverse Events associated with any other BI drug

The investigator is encouraged to report all adverse events related to any BI drug other than the Spiolto® Respimat® according to the local regulatory requirements for spontaneous AE reporting at the investigator's discretion by using the locally established routes and AE report forms. The term AE includes drug exposure during pregnancy, and, regardless of whether an AE occurred or not, any abuse, off-label use, misuse, medication error, occupational exposure, lack of effect, and unexpected benefit.

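### Do the SAP safety tables promise all-cause adverse event incidence that the study does not collect?

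*SAP*

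**What the plan says.** **Collection.** Protocol 11.2 sets what the investigator must enter in the eCRF: every ADR, serious or not, and "all AEs with fatal outcome (serious adverse events"). Other events stay at the site: "The investigator shall maintain and keep detailed records of all AEs in their patient files". The expedited reporting table in the same section lists, besides ADRs and pregnancies, "All AEs with fatal outcome in patients exposed to Spiolto® Respimat". The safety row of the visit chart in protocol 9.2.3 reads "Safety: Adverse Drug Reactions (serious and non-serious), fatal AE, pregnancy".

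**Definition.** Protocol 11.1 makes seriousness independent of causality: "A serious adverse event is defined as any AE which" meets one of the listed criteria.

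**Analysis.** Protocol 9.7.1 introduces its list of analysed data with "The analyses will relate to the following data as recorded in the eCRF", and that list names ADRs, fatal AEs and pregnancies. A second, shorter list in the same section gives the safety parameters as AEs and SAEs, followed by ADRs, with no stated limit. SAP 5.2.7 relates the incidence of adverse reactions and AEs to the number of treated patients.

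**Tables.** SAP 6.5 states the restricted scope in its first sentence, just above Table 26. Table 26 contains the rows for patients with a serious AE (broken down by six criteria) and "Patients with serious AE leading to discontinuation". Tables 27 and 32 are titled for AEs and serious AEs in general. None of the three has a scope footnote.

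**The concern.** By the protocol's own definition an SAE need not be related to the drug. A reader who sees a serious AE row next to a serious drug-related AE row will therefore take the difference as unrelated serious events of every kind. Under the minimum collection rule, that difference holds only unrelated fatal events. A hospitalisation judged unrelated and survived need not be in the database at all. If the table were read as all-cause, the serious event rate would look lower than it was.

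Two smaller points pull the same way. SAP Tables 3 and 16 list an adverse event as a reason for a missed visit 2 or for leaving the study, without asking whether it was related, so their counts may not match Table 26. Table 33 counts pregnancies among patients with an AE, whereas protocol 11.2 has a pregnancy without a reportable AE documented only on its own form.

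**Working it through.** No figure in the plan bears on this point, so the check is a comparison of wording followed by simple set reasoning.

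**Where each scope appears**

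| Restricted scope (ADRs, fatal AEs, with or without pregnancies) | Wording without a limit |
|---|---|
| Protocol abstract, variables | Protocol 9.7.1, safety-parameter list and the sentence on AE occurrence |
| Protocol 9.2.3 visit chart | SAP 5.2.7 |
| Protocol 9.3.2.2 | SAP Table 26, two serious-AE rows |
| Protocol 9.7.1, list of eCRF data | SAP Table 27 |
| Protocol 9.10.2.1 source documents | SAP Table 32 |
| Protocol 11.2, collection rule and reporting table | |
| SAP 5.2.5 | |
| SAP 6.5, opening sentence | |

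The left column contains every statement of what is collected, and the sentence that governs the safety tables. The right column contains labels and summary wording only.

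**Are the two lists in protocol 9.7.1 in conflict?** Under the restricted scope an unrelated death is an AE and an SAE but not an ADR. A list that named only ADRs would leave it out, so an item for AEs and SAEs is needed even when collection is limited. The wording is loose, but both lists can be met from the same data.

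**Rows of Table 26.** Below the number of patients there are 5 main rows and 6 seriousness criteria, 5 + 6 = 11 in all. Three main rows are marked drug-related (drug-related AE; drug-related AE leading to discontinuation of trial drug; serious drug-related AE). Two are not (serious AE; serious AE leading to discontinuation), and 3 + 2 = 5. There is no row for any AE, so in Table 26 the unrestricted reading touches only the serious rows. Tables 28 to 31 are all labelled drug-related and match what is collected.

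**What the rows hold under protocol 11.2**

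- Recorded events = ADRs + unrelated fatal AEs.
- Table 27 = the same set.
- Serious AE rows and Table 32 = serious ADRs + unrelated fatal AEs.
- Patients with a serious AE minus patients with a serious drug-related AE = patients with an unrelated fatal AE and no serious ADR.

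This is the content announced in the first sentence of SAP 6.5. A footnote would leave each of these sets unchanged. If a site enters more than the minimum, the extra event is counted and can be identified, because the listing in Table 65 has a column for relationship to the study drug.

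**The smaller points**

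- Table 3 covers all screened patients and reasons for missing visit 2 or discontinuing. Table 16 covers leaving the study. The drug-related discontinuation row of Table 26 concerns stopping the trial drug. These are different events, and for Table 3 a different population, so the counts could differ even with complete AE collection.
- The public table list passes from Table 33 to Table 48, and the contents place SAP 6.5.4 on page 46 and the references on page 54. A missing pregnancy shell therefore cannot be inferred from the text available. Pregnancy is also an exclusion criterion, and patients are aged 40 or over.

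**The case for a change.** The strongest case for acting is that tables travel without their text. Table 26 or 32 may be copied into a results posting or a paper, where the first sentence of SAP 6.5 does not follow it. The reader then has only the protocol's broad SAE definition, under which a hospitalisation row looks like all hospitalisations. Repeating the scope under three tables and two listings would cost almost nothing, and one SAP sentence could tie the 9.7.1 safety parameters to the 11.2 rule.

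What stands is that the labels are looser than the collection rule, and that a table taken out of its section could be misread. What does not stand is that the plan is silent or commits to something it cannot deliver. The scope is stated at the head of the section that contains the tables, and the protocol ties its analyses to recorded data. An analyst following the SAP produces the same numbers with or without the note, and a report author has the scope sentence to hand. Splitting fatal events by relationship would add nothing new, since Table 65 lists relationship and outcome for every event.

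**Conclusion.** No change to the plan is called for. This is a labelling detail that those writing the report can handle from text already in SAP 6.5. It affects two of five main rows in Table 26, and Tables 27 and 32. It alters no safety count, no denominator and no efficacy result. How far the serious-AE rows fall short of an all-cause count cannot be stated, because the documents give no rate of unrelated non-fatal serious events; the shortfall may be zero, and the plan does not undertake to report that quantity.

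The conclusion rests on two assumptions: that sites follow at least the minimum rule of protocol 11.2, and that the report keeps the scope sentence with the safety section. If the tables are published separately, their author should carry the scope with them as ordinary good practice.

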6.5.1. Adverse events

Table 27. AE according to MedDRA-SOC and PT - Treated Set (TS)		
	Patients n (%)	Events n (%)
Presence of AE during the study n (%)		
SOC 1		
PT1		
PT2		
...		
SOC 2		
PT1		

Table 27. AE according to MedDRA-SOC and PT - Treated Set (TS)

	Patients n (%)	Events n (%)
PT2		
...		
...		

6.5.2. Drug-related adverse events

Table 28. Summary Drug-related adverse events - Treated Set (TS)

	Events n (%)
Total drug-related adverse events	
Serious Drug-related adverse event	
Non-Serious drug-related adverse event	

Table 29. Serious Drug-related adverse events - Treated Set (TS)

	Events n (%)
Total Serious drug-related adverse events	
Description	
SOC 1	
PT1	
PT2	
...	
SOC 2	
PT1	
PT2	
...	
...	

Table 30. Non-Serious Drug-related adverse events - Treated Set (TS)

	Events n (%)
Total Non-Serious drug-related adverse events	
Description	
SOC 1	
PT1	

Table 30. Non-Serious Drug-related adverse events - Treated Set (TS)	
	Events
	n (%)
PT2	
...	
SOC 2	
PT1	
PT2	
...	

Table 31. Outcome Drug-related adverse events - Treated Set (TS)	
	Events
	n (%)
Total drug-related adverse events	
Outcome	
Recovered/resolved	
Not recovered/resolved	
Recovered/resolved with sequelae	
Exitus	
Unknown	

6.5.3. Serious Adverse Events

Table 32. Characteristics of Serious adverse events - Treated Set (TS)	
	Total
	n (%)
Total Serious adverse events	
Description	
SOC 1	
PT 1	
...	
SOC 2	
...	

6.5.4. Pregnancy

Table 33. Patient pregnant at AE - Treated Set (TS)	
	n (%)
Total Patient at AE	
Yes	
No	
Not applicable	

All AEs reported in the study, together with the provided characteristics of intensity, severity, treatment administered to treat the AR, action taken, causal relationship with study treatment and outcome will be listed in the ANNEX 7. REPORTED ADVERSE EVENTS.

8. ANNEX

8.1. ANNEX 1. DB DEBUGGING

The DB debugging process, which is established in the Data Management Plan (DMP) will be described in this annex.

The description of debugging and/or variables generated during the data analysis process will also be described.

Table 48. Validation during data entry: Selection criteria

	Variables	Visit	Data block	Inconsistency in CRF	Message / Warning	Can be validated
						No
						No

[Note, if applicable]

Table 49. Debugging performed during the statistical analysis

Patient	Visit	Variable	Data block	Inconsistency in DB	Action taken

[Note, if applicable]

Table 50. New variables created for the preparation of the results report

New variable	Data block	Description

8.2. ANNEX 2. DETAILS OF THE NON-ASSESSABLE PATIENTS

This section will include the list of non-assessable patients for this study:

Table 51. Description of the TS non-assessable patients			
Patient No.	Inclusion criterion 1	Informed consent date	Patient with no data on treatment with Spiolto® Respimat®

Table 52. Description of the FAS non-assessable patients						
Patient No.	Inclusion criterion 1	Informed consent date	Patient with no data on treatment with Spiolto® Respimat®	Patients with PF-10 assessable at baseline visit only	Patients with PF-10 assessable at visit after 6 weeks only	Patients without PF-10 assessable at baseline visit and at visit after 6 weeks

8.3. ANNEX 3. RECORDED CONCOMITANT DISEASES

Concomitant diseases recorded throughout the study, according to Table 12 (concomitant diseases at the baseline visit); and Table 18 (new concomitant diseases after 6 weeks) will be listed in the following tables.

Table 53. Concomitant diseases at baseline visit (visit 1) – Treated Set (TS)

	Total ¹	Total with CDs ²	Ongoing ²
Does the patient present with any COPD-related concomitant diseases? n (%)			
Yes			
No			
Cardiovascular disease n (%)			
Yes			
No			
Type of cardiovascular disease (diagnosis)³			
Diagnosis 1			
Diagnosis ...			
Diabetes mellitus n (%)			
Yes			
No			
Musculoskeletal disorders n (%)			
Yes			
No			
Type of musculoskeletal disorder (diagnosis)⁴			
Diagnosis 1			
Diagnosis ...			
Kidney diseases n (%)			
Yes			
No			
Type of kidney disease (diagnosis)⁵			
Diagnosis 1			
Diagnosis ...			
Liver diseases n (%)			
Yes			
No			
Type of liver disease (diagnosis)⁶			
Diagnosis 1			
Diagnosis ...			

Table 53. Concomitant diseases at baseline visit (visit 1) – Treated Set (TS)

	Total ¹	Total with CDs ²	Ongoing ²
Osteoporosis n (%)			
Yes			
No			
Gastro-oesophageal reflux (GOR) n (%)			
Yes			
No			
Lung cancer n (%)			
Yes			
No			
Other n (%)			
Yes			
No			
Type of liver disease (diagnosis)⁷			
Diagnosis 1			
Diagnosis ...			

Note: Concomitant disease (CD). A patient could have more than one CD

¹ Of the total number of treated patients (n=xx)

² Of the total number of patients with CDs (n=xx)

³ In the event of cardiovascular disease (n=xx)

⁴ In the event of osteoporosis (n=xx)

⁵ In the event of kidney diseases (n=xx)

⁶ In the event of liver diseases (n=xx)

⁷ In the event of other concomitant diseases (n=xx)

Table 54. Duration of concomitant diseases at baseline visit (months) – Treated Set (TS)

	n	mean	SD	(95% CI)	Median	[P25-P75]	Min	Max
Cardiovascular disease								
Diagnosis 1								
Diagnosis ...								
Diabetes mellitus								
Musculoskeletal disorders								
Diagnosis 1								
Diagnosis ...								
Kidney diseases								
Diagnosis 1								
Diagnosis ...								
Liver diseases								

Diagnosis 1
Diagnosis ...
Osteoporosis
Gastro- oesophageal reflux (GOR)
Lung cancer
Other
Diagnosis 1
Diagnosis ...

Note: n according to each of the concomitant diseases

Table 55. New concomitant diseases after 6 weeks (visit 2) – Treated Set (TS)

	Total ¹	Total with new CD ²	Ongoing ²
Does the patient have any new concomitant diseases with respect to those of the last visit? n (%)			
Yes			
No			
Cardiovascular disease n (%)			
Yes			
No			
Type of cardiovascular disease (diagnosis)³			
Diagnosis 1			
Diagnosis ...			
Diabetes mellitus n (%)			
Yes			
No			
Musculoskeletal disorders n (%)			
Yes			
No			
Type of musculoskeletal disorder (diagnosis)⁴			
Diagnosis 1			
Diagnosis ...			
Kidney diseases n (%)			
Yes			
No			
Type of kidney disease (diagnosis)⁵			
Diagnosis 1			
Diagnosis ...			

Table 55. New concomitant diseases after 6 weeks (visit 2) – Treated Set (TS)

	Total ¹	Total with new CD ²	Ongoing ²
Liver diseases n (%)			
Yes			
No			
Type of liver disease (diagnosis)⁶			
Diagnosis 1			
Diagnosis ...			
Osteoporosis n (%)			
Yes			
No			
Gastro-oesophageal reflux (GOR) n (%)			
Yes			
No			
Lung cancer n (%)			
Yes			
No			
Other n (%)			
Yes			
No			
Type of liver disease (diagnosis)⁷			
Diagnosis 1			
Diagnosis ...			

Note: Concomitant disease (CD). A patient could have more than one CD

¹ Of the total number of treated patients (n=xx)

² Of the total number of patients with new CD (n=xx)

³ In the event of cardiovascular disease (n=xx)

⁴ In the event of osteoporosis (n=xx)

⁵ In the event of kidney diseases (n=xx)

⁶ In the event of liver diseases (n=xx)

⁷ In the event of other concomitant diseases (n=xx)

Table 56. Duration of new concomitant diseases after 6 weeks (months) – Treated Set (TS)

	n	mean	SD	(95% CI)	Median	[P25-P75]	Min	Max
Cardiovascular disease								
Diagnosis 1								
Diagnosis ...								
Diabetes mellitus								
Musculoskeletal disorders								
Diagnosis 1								

Table 56. Duration of new concomitant diseases after 6 weeks (months) – Treated Set (TS)

	n	mean	SD	(95% CI)	Median	[P25-P75]	Min	Max
Diagnosis ...								
Kidney diseases								
Diagnosis 1								
Diagnosis ...								
Liver diseases								
Diagnosis 1								
Diagnosis ...								
Osteoporosis								
Gastro-oesophageal reflux (GOR)								
Lung cancer								
Other								
Diagnosis 1								
Diagnosis ...								

Note: n according to each of the concomitant diseases

